Assuming 20% loss-to-follow-up in the ChiLDREN START study and in this study (i.e., 23 subjects in the IVIG group and 56 subjects in the START placebo group), there is 74% power with a one-sided Type I error rate of 10% to detect a difference of 25.5% -- a 50% improvement with treatment (i.e., 76.5% in the IVIG group and 51% in the placebo group). This is based on Fisher's exact test for two proportions (SAS 9.3). The corresponding power for sample sizes of 29 and 70 in the IVIG and placebo groups (if there were no drop-outs) is 82%. Alternatively, we have 80% power to detect a difference of 28% in this outcome (79% in the IVIG group and 51% in the placebo group) with sample sizes of 23 and 56 in the IVIG and placebo groups, reflecting a possible 20% drop-out rate. The corresponding power for sample sizes of 29 and 70 in the IVIG and placebo groups, if there were no drop-outs, is 88%.

Hypothesis 2b states that treatment with IVIG will improve the probability of an infant having good bile flow 360 days after HPE for BA as evidenced by the proportion of subjects who survive 360 days after HPE with both their native liver and serum total bilirubin <1.5 mg/dL at 360 days after HPE. In the prospective PROBE study, approximately 68% of BA patients who had an HPE by 4 months of age survived to 12 months of age with their native liver and had serum bilirubin <1.5 mg/dL. We assume that a comparable proportion of placebo subjects in START will have this outcome. There is 76% to 85% power to detect a 33% relative improvement in this outcome with the anticipated sample sizes described above (ranging from 23 and 56 in the IVIG and placebo groups, respectively, when adjusting for 20% drop-out, to 29 and 70 in the IVIG and placebo groups, respectively, if there were no drop-out), based on Fisher's exact test for two proportions (SAS 9.3) and a one-sided Type I error rate of 10%. This relative

improvement corresponds to approximately 90% of the IVIG subjects having improved bile flow at 360 days after HPE, compared to an anticipated 68% in START placebo patients.

Hypothesis 3 states that survival with native liver at 360 days following HPE is improved in infants treated with IVIG compared to historical controls. Since 68% of PROBE BA patients who had their HPE by 4 months of age survived to 12 months of age with their native liver and with serum total bilirubin < 1.5 mg/dL, the power calculations for Hypothesis 2b apply identically to Hypothesis 3.

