# Aim 2: To obtain preliminary evidence whether IVIG therapy is associated with lower serum bilirubin concentration after HPE.

*Hypothesis 2a*: The probability of an infant having good bile drainage at 90 and 180 days after HPE (as defined by survival 90 or 180 days after HPE with both their native liver and serum total bilirubin level <1.5 mg/dL at 90 or 180 days after

HPE) will be greater in infants who are treated with IVIG compared to historical controls.

The proportions of subjects who have survived with their native liver and have bilirubin <1.5 mg/dL will be calculated at both time points. Each proportion will be compared to that of historical controls from the placebo group in the START study using Fisher's exact test. Given that previous studies have found age at HPE to be predictive of later clinical outcomes, we will perform an exploratory logistic regression analysis, including IVIG treatment (vs control) and age at HPE as covariates. Odds ratios and one-sided 90% Wald upper confidence bounds will be presented.

*Hypothesis 2b*: The probability of an infant having good bile drainage at 360 days after HPE (as defined by survival 360 days after HPE with both their native liver and serum total bilirubin level <1.5 mg/dL at 360 days after HPE) will be greater in infants who are treated with IVIG compared to historical controls.

The same methods will employed as in Hypothesis 2a.

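### At the day-360 target rate, the age-adjusted odds ratio and its Wald bound cannot be computed in 5–9% of trials, namely those in which every IVIG infant succeeds

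*Protocol*

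**What the plan says.** Under Aim 2, Hypothesis 2a, section 5.3 of the protocol sets the main comparison: "Each proportion will be compared to that of historical controls from the placebo group in the START study using Fisher's exact test". Because age at HPE is known to predict outcome, it then adds a model: "we will perform an exploratory logistic regression analysis, including IVIG treatment (vs control) and age at HPE as covariates". The reporting rule for that model is "Odds ratios and one-sided 90% Wald upper confidence bounds will be presented".

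For day 360 (Hypothesis 2b) the section says only: "The same methods will employed as in Hypothesis 2a".

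The day-360 planning values are in section 5.2.2. On the IVIG target it states: "improvement corresponds to approximately 90% of the IVIG subjects having improved bile flow at 360 days after HPE". The control rate, taken over from an earlier cohort, is worded there as "compared to an anticipated 68% in START placebo patients". The group sizes are given as "ranging from 23 and 56 in the IVIG and placebo groups, respectively, when adjusting for 20% drop-out, to 29 and 70". The stated power of 76% to 85% is for a one-sided 10% Fisher's exact test. The protocol states no power or decision rule for the logistic model. It also says nothing about what to report if one group has no failures.

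**The concern.** A 90% success rate in 23 to 29 infants means 2 to 3 expected failures (0.10 × 23 = 2.3; 0.10 × 29 = 2.9). With so few, a count of zero is a realistic outcome. When it occurs, the treatment indicator separates the data: the likelihood keeps rising as the treatment coefficient grows, and adding age to the model does not stop this. The maximum-likelihood odds ratio is infinite, and the Wald standard error reflects only where the software stopped iterating.

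The comparison is with historical controls, and this model is the only planned Aim 2 analysis that adjusts for age at HPE. Its estimate disappears in the trials most favourable to IVIG, where a reader would most want to know whether age explains the difference.

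**Working it through.** **Inputs (section 5.2.2).** Day-360 success is about 90% with IVIG and 68% with START placebo. The sizes are 23/56 (20% drop-out) and 29/70 (none), and the level is one-sided 10%, so z = 1.2816. The exact relative improvement gives 0.68 × 1.33 = 90.4%.

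**The plan's own figure first.** Full enumeration of the two binomials for one-sided Fisher p ≤ 0.10:

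| IVIG vs control | 23/56 | 29/70 |
|---|---|---|
| 90% vs 68% | 74.5% | 84.1% |
| 90.44% vs 68% | 76.4% | 85.7% |
| Stated in the protocol | 76% | 85% |

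The stated power reproduces.

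**How often the odds ratio is infinite.** P(all IVIG infants succeed) = pⁿ.

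| IVIG success rate | n = 23 | n = 29 |
|---|---|---|
| 90% (day-360 target) | 8.9% | 4.7% |
| 85% (for comparison) | 2.4% | 0.9% |
| 79% (day-180 alternative) | 0.4% | 0.1% |
| 76.5% (day-180 target) | 0.2% | 0.04% |

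**What the two methods report.** With a successes of n₁ on IVIG and c of n₀ in controls, the Wald bound is log OR ± 1.2816 × √(1/a + 1/(n₁−a) + 1/c + 1/(n₀−c)). It is undefined when a = n₁. Without covariates, Firth's method amounts to adding ½ to each cell. Its profile bound is the set of log odds ratios for which twice the drop in penalised log-likelihood is at most 1.2816² = 1.642. With 38/56 control successes (68%), the odds ratios and one-sided 90% lower and upper bounds are:

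| IVIG successes | Wald | Firth, profile |
|---|---|---|
| 23/23 | infinite; no bound | 22.6 (5.1; 302) |
| 22/23 | 10.4 (2.67; 40.6) | 7.2 (2.61; 27.3) |

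An age-adjusted maximum-likelihood fit of the 23/23 case, with ages made up for illustration, returned a log odds ratio of about 23 with a standard error of about 16,500. Neither Wald bound from it means anything.

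**How often a lower bound excludes no effect.** This is an unadjusted full enumeration in which all-success trials count as uninformative for Wald.

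| Rates, sizes | Wald | Firth |
|---|---|---|
| 90% vs 68%, 23/56 | 75.2% | 81.5% |
| 90% vs 68%, 29/70 | 84.2% | 87.9% |
| Null 68% vs 68%, 23/56 | 10.1% | 9.9% |
| Null 68% vs 68%, 29/70 | 10.1% | 9.4% |
| 76.5% vs 51%, 23/56 | 81.5% | 81.7% |
| 76.5% vs 51%, 29/70 | 87.7% | 87.1% |

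At day 360 the gain is 6.3 and 3.7 points, and null rejection is no higher. All of the gain comes from the all-success trials. Leaving those out, Firth excludes no effect slightly less often than Wald: 81.5 − 8.9 = 72.6% against 75.2%, and 87.9 − 4.7 = 83.2% against 84.2%.

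**Age-adjusted check.** The protocol gives no age effect, so log odds ratios of 0, −0.5 and −1.0 per standard deviation were assumed. Simulation gave 74–77% (Wald) and 81–85% (Firth) at 23/56, and 84–87% and 88–92% at 29/70. The pattern is the same.

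**The case against.** The strongest reply is that the hypothesis is tested by Fisher's exact test and the logistic model is labelled exploratory. This stands. A reader might infer from the 4 to 6 point difference that the trial loses planned power. The protocol does not support that reading, because the 76–85% belongs to Fisher's test. Given that all IVIG infants succeed, that test rejects with probability 0.9998 at 23/56 and above 0.9999 at 29/70. The two group proportions also remain reportable.

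A reader might also infer that Wald bounds fail whenever nearly all IVIG infants succeed. They do not. With one failure the lower bounds almost agree (2.67 and 2.61), and against a likelihood-ratio test Wald rejects essentially as often (99.8% and 99.9% at 23/56). The failure needs zero failures, so it is confined to day 360 at a rate near 90%.

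The size of the difference depends on the comparator: about 0 against Fisher, 4 to 6 points against Firth, and 6 to 9 against the likelihood ratio. It also concerns a lower bound, whereas section 5.3 names an upper one, for which coverage is about the same under both methods (89–90% for Wald, about 88.5% for Firth). The infinite estimate affects either side.

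Finally, a fallback for separation is often left to the statistical analysis plan, which is not shown here. That would excuse silence in the protocol. But the protocol names the Wald method itself, so the choice is open to comment.

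**Conclusion.** The point holds as a minor one. The bound that section 5.3 specifies cannot be computed in 8.9% (n = 23) or 4.7% (n = 29) of trials at the protocol's own day-360 target. What is lost there is the only age-adjusted Aim 2 estimate. No planned test or stated power is affected.

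The size rests on a true IVIG rate of about 90%, independent infants, and 23 to 29 of them evaluable. At 85% the frequency falls to 2.4% or 0.9%, and at the day-180 planning rates to 0.4% or less. The 75.2% against 81.5% and 84.2% against 87.9% are unadjusted and describe how often a lower bound would exclude no effect. They should be quoted only in that sense.

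**What to change.** In section 5.3, Aim 2, replace the Wald bounds by Firth penalised-likelihood odds ratios with one-sided 90% profile penalised-likelihood bounds for the logistic models. The change matters at day 360. Using it at days 90 and 180 as well keeps one method across time points and changes little there.

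The cost is one phrase in the protocol and one option in the logistic procedure. The odds ratios shrink towards 1, usually slightly but visibly when failures are very few (10.4 to 7.2 in the one-failure example). Fisher's exact test, the sample size and the power statement stay as they are.

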# Aim 3: To obtain preliminary evidence whether IVIG treatment after HPE will improve survival without liver transplantation at 360 days after HPE.

**Hypothesis 3:** Survival without transplantation will be greater at 360 days after HPE in infants treated with IVIG compared to historical controls.

The proportion of subjects who have survived with their native liver at 360 days after HPE will be estimated among the IVIG treated subjects and the historical placebo controls by Kaplan-Meier methods. Time to liver transplantation or death will be calculated as the number of days from the day of HPE to the first of liver transplantation, death, or last day of follow-up without these events. Subjects will be censored if these events don't occur by the last day of study follow-up. The difference between the two Kaplan-Meier estimates will be computed and a 90% upper confidence bound will be calculated for the difference, using the pooled variance (based on each group's standard error calculated with Greenwood's formula).

#### Aim 4: To explore mechanisms of action of IVIG treatment in biliary atresia.

**Hypothesis 4**: IVIG treatment in BA is associated with an increase in circulating regulatory T-Cells and reduction of inflammatory cytokines and specific autoantibodies.

The percentage and absolute numbers (with corresponding two-sided 80% CIs) of circulating regulatory T-cells, circulating cytokine levels and IgM anti-enolase autoantibody levels (and two-sided 80% CIs) (detailed in section 4.3.2) will be calculated at each time point measured and each will be compared to the baseline values before

IVIG administration using the paired *t* or nonparametric Wilcoxon signed rank tests. In addition, trends over time (prior to IVIG and 60, 90, 180 and 360 days after HPE) will be explored using linear or non-linear methods. Changes from baseline in these parameters will be compared between those subjects who achieve normal serum bilirubin at 180 days after HPE and those that do not, and between those that survive with native liver at 360 days after HPE and those that do not by the 2-sample *t* or nonparametric Wilcoxon rank sum test. Although the hypothesis is stated in terms of increases or decreases, thus suggesting one-sided CIs, two-sided 80% CIs will be presented that allow testing of both increases or decreases for each parameter. No adjustments for multiple comparisons will be made, owing to the exploratory and hypothesis-generating nature of this aim.

#### 5.4. Data Management

The Statistical Analysis of Biomedical and Educational Research (SABER) unit in the Department of Biostatistics at the University of Michigan will serve as the data coordinating center (DCC) and is responsible for data management and analysis. The DCC provides and maintains computerized data management systems with capabilities for central data entry, remote site data entry, editing, modifying, and reporting of data.

#### 5.4.1. Data Collection

The DCC maintains a password-protected website for all studies in ChiLDREN. All transmissions to and from the website are encrypted using SSL. Each subject is identified by a study specific subject identification number. Data collection does not contain any personal subject identifiers, except dates, such as date of birth, which are necessary for research purposes. An investigator and/or study coordinator can only view data in the study database from his/her clinical site.

#### 5.4.2. Quality assurance

The DCC staff monitors and reports on data quality, protocol adherence, and recruitment status. The DCC staff conducts site visits for data review on a periodic basis for quality assurance. During these visits the clinical monitor reviews the regulatory file, checks all informed consent documents, and reviews procedures with the site coordinators. Interim site visits may be made to centers with low compliance or high error rates. The DCC is responsible for reporting on safety and data quality and timeliness to the NIDDK and the NIDDK appointed Data and Safety Monitoring Board. The DCC staff assists with the preparation of study materials, including the final protocol and the manuals of operation for each study to optimize clinical site performance in study conduct.

#### 5.4.3. Training

The DCC staff will verify that clinical site staff are trained and/or certified in study conduct and procedures. The DCC has developed general and project-specific manuals of operations to assist investigators and study coordinators in the conduct of this trial, entering and transferring data, and collecting, processing and shipping samples. Clinical coordinators will participate in a protocol initiation and electronic data capture system training session provided by the DCC. The Project Manager/Clinical Monitor will review the study protocol and data entry system, and check all regulatory documents prior to site initiation.

# 6. HUMAN SUBJECTS RESEARCH CONSIDERATIONS

#### 6.1. Risks to study subjects

#### 6.1.1. Involvement of subjects

Subjects will be recruited into this study at the time that BA is suspected and exploratory surgery is scheduled or within 3 days following HPE. Subjects will be treated with three infusions of IVIG and followed as outpatients for 360 days following HPE.

# 6.1.2. Planned duration of the entire study

Based on the anticipated enrollment of 29 subjects per year by the CHILDREN centers involved in this trial, we estimate completing enrollment within 18-24 months, with an additional 6 months to gather primary outcome follow-up data on subjects enrolled in the final year. However, the testing of secondary outcome measures (such as survival with native liver at 360 days after HPE) will extend the overall duration of the study to 2.5 to 3 years from the initiation of enrollment.

#### 6.1.3. Duration of participation for each subject

Each subject will remain in the clinical trial for 360 days. The use of IVIG will be limited to the first 60 days. This will be followed by very close follow-up in outpatient clinics for an additional 300 days (total 360 days post-HPE follow-up). Subjects will be seen clinically as needed (by either their primary care provider or by a gastroenterologist at the study site) for evaluation and management of medical problems that may arise because of the natural progression of liver disease in affected children.

#### 6.1.4. Sources of research material

Subjects will be recruited from the pool of infants with jaundice referred to or evaluated by the outpatient and inpatient services at the CHILDREN clinical centers. Research material will include clinical and laboratory data, physical findings, and data collected for this study.

#### 6.1.5. Potential risks to subjects

There are three potential sets of risks associated with this clinical trial. The first set derives from blood draws, and includes amount of blood, as well as pain, bruising, or superficial phlebitis. Most of the scheduled venipunctures are part of routine tests necessary for the proper care of infants following HPE; serum levels of electrolytes, BUN and creatinine and IgG will be included to monitor for possible adverse effects of IVIG treatment. The second set of risks derives from expected adverse events associated with IVIG administration or from the other standard of care medications. The third set of risks derives from peripheral IV insertion and use. Several of these are discussed in more detail:

# 6.1.5.a. Amount of blood

Blood is drawn as part of the routine clinical care of the BA patient following HPE, to monitor for liver function and adverse events. Blood will also be drawn for mechanistic research studies for this clinical trial. The cumulative amount of blood to be drawn for research purposes is outlined in Table 5 below.

Visit	Amount in ml drawn for research at the visit	Maximum research blood draw in ml within 2-month period	Maximum research blood draw in ml within 3-month period	
Initial	5.0	5.0	5.0	
2 weeks post op	1.0	6.0	6.0	
30 days post op	1.0	7.0	7.0	
60 days post op	6.0	13.0	13.0	
90 days post op	6.0	12.0	19.0	
180 days post op	6.0	6.0	6.0	
270 days post op	2.0	2.0	2.0	
360 days post op	6.0	6.0	6.0	
At liver transplant	1.0			

## Table 5. Total amount of blood drawn from infants in the clinical trial

**NOTE:** Blood volume for clinically indicated tests: Approximately 2.2-3.3 ml of blood may be removed from the child at each visit to evaluate hepatic function, , PT/INR and complete blood count and differential. More may be withdrawn to perform additional clinically indicated lab tests.

At each follow up visit, 0.6 ml of blood will be drawn for a complete blood count and differential, 1.0 ml for hepatic function tests, and 0.6-1.7 ml for a PT/INR. 1.0 ml will be drawn for safety related serum electrolytes, BUN and creatinine. At the initial blood draw prior to IVIG and follow-up visits at 60, 90, 180, and 360 days post-HPE, 4.0 ml of blood will be drawn for mechanistic research studies. An additional 1.0 ml of blood will be drawn at 60, 90, 180, 270 and 360 days post-HPE for serum IgG level.

# 6.1.5.b. Side effects of IVIG

The second set of potential risks derive from reported side effects of IVIG which include headache, irritability, flu-like symptoms, fever, nausea, fluid overload, allergic reactions, local infusion site reactions, viral contamination of the product, interference with live vaccines, aseptic meningitis, renal dysfunction, thrombotic events, hypotension and hypoglycemia. All of these side effects are uncommon or not serious in infants and young children (45-46). Despite these potential adverse events, this clinical trial is justified by the devastating nature of BA on the well-being of affected children and on the progression to end-stage liver disease in most patients with the prospects for improved care of future patients with BA if IVIG is found to be beneficial. In this context, IVIG treatment may result in reduced hepatic inflammation, improved bile flow, allow for better

growth, and increase long-term survival with the native liver. To minimize potential adverse events to subjects, it is recommended that the IVIG be diluted to a 5% solution when administered into a peripheral vein if this is acceptable by the local institutional policy. In addition, the clinical site staff will monitor all subjects closely during each IVIG infusion for side effects, and promptly adhere to their institutional action plan and that outlined in the Data Safety Monitoring Plan (DSMP) if side effects are identified (see Section 7.4).

## 6.1.6. Alternative treatments considered

IVIG treatment is being considered in this study as an adjuvant treatment for children with biliary atresia. There is currently no other available treatment for BA of proven efficacy and safety that is not being used in this trial. At present, other adjuvant therapies may be under development, such as anti-inflammatory agents that target specific components of the immune system, anti-fibrogenic medications and others. We are aware of only one ongoing trial of one such medication (corticosteroids trial of ChiLDREN – the START study, NIDDK IND #71411 ) that has fully enrolled its participants and from which results may become available prior to completion of the PRIME trial. These results may impact the PRIME study and adjustments may need to be made in the PRIME protocol after the START results are finalized. Preventive approaches to biliary atresia may also become available in the future as new discoveries are made on pathogenic agents causing biliary atresia.

#### 6.2. Adequacy of protection against risks

## 6.2.1. Plan to protect subjects/mitigate risks

Subject confidentiality will be maintained by entering the data on the subject into a research database through a password-protected website (using SSL) maintained by the DCC. In the research database, subjects will not be identified by name, but by study numbers only. All consent documents will adhere to the HIPAA regulations, and will use the accepted terminology mandated by each site.

Careful attention to inclusion and exclusion criteria will also protect subjects against potential adverse effects of IVIG treatment.

Blood will be drawn whenever possible at times of venipuncture for routine care or when intravenous lines are in place to reduce the risks of venipuncture.

